5.1. Inclusion Criteria

1. Age $\geq 22^c$ years, ≤ 75 years
2. 7 day recall of Average Low Back Pain VAS of ≥ 6.0 cm and ≤ 9.0 cm at baseline (on a 10cm scale)
3. Oswestry Disability Index score $\geq 21\%$ and $\leq 60\%$ at the Baseline Visit.
4. Chronic Low Back Pain defined as pain and discomfort localized below the costal margin and above the inferior gluteal fold (with or without referred leg pain) that has persisted >90 days prior to the Baseline Visit, which has resulted in pain in at least half of the days in the 12 months prior to the Baseline Visit, as reported by the Subject.
5. Evidence of lumbar multifidus muscle dysfunction by the Prone Instability Test (PIT).
6. Continuing low back pain despite >90 days of medical management including:
 - a. At least one attempt of physical therapy treatment for low back pain, which may optionally be accomplished over multiple episodes or flare-ups of low back pain.
NOTE 1: Subjects who start a physical therapy program but are unable to complete it are still eligible with regards to this inclusion criterion.
NOTE 2: Subjects who participated in a physical therapy program in the past since the onset of low back pain but are unwilling or unable to participate in a new physical therapy program are still eligible with regards to this inclusion criterion;
 - b. For Subjects with medications prescribed and used for chronic low back pain, usage shall be at a stable dose in the 30 days prior to the Baseline Visit as reported by the Subject.
NOTE 3: A stable dose means the Subject reports no significant change in regular use of medications, which may include PRN use, in the 30 days prior to the Baseline Visit.
7. Be willing and capable of giving Informed Consent
8. Ability to comply with the instructions for use and to operate ReActiv8, and to comply with this Clinical Investigation Plan.
9. Suitable for ReActiv8 surgery as determined by the implanting physician prior to inclusion.

5.2. Exclusion Criteria

1. BMI > 35
2. Back Pain characteristics:
 - a. Any surgical correction procedure for scoliosis at any time, or a current clinical diagnosis of moderate to severe scoliosis (Cobb angle $\geq 25^\circ$).
 - b. Lumbar spine stenosis, as defined by an anterior-posterior diameter of the spinal canal of <10 mm in Subjects with lower extremity pain.
 - c. Neurological deficit possibly associated with the back pain (e.g. foot drop).
 - d. Back pain due to pelvic or visceral reasons (e.g.: endometriosis or fibroids) or infection (e.g.: post herpetic neuralgia).
 - e. Back pain due to inflammation or damage to the spinal cord or adjacent structures (e.g. arachnoiditis or syringomyelia).

^c As per the FDA definition of an adult

- f. Pathology seen on MRI that is clearly identified and is likely the cause of the CLBP that is amenable to surgery.
- g. Back pain due to vascular causes such as aortic aneurysm and dissection.
3. An independent assessment of any current indication for back surgery according to appropriate guidelines, or has indications for back surgery but cannot undergo surgery for other reasons.
4. Leg pain described as being worse than back pain, or radiculopathy (neuropathic pain) below the knee.
5. Source of pain is the sacroiliac joint as determined by the Investigator.
6. Drug use per Subject report as follows:^d
 - a. Current baseline use of >120mg oral morphine equivalent per day of opioids.
 - b. Current use of breakthrough dose of >60mg oral morphine equivalent per day
 - c. Current requirement of opioids for treatment of a condition other than low back pain.
 - d. History of any substance abuse at any time in the five years prior to the Baseline Visit.
 - e. Currently taking >15mg Diazepam per day or equivalent. (See Table 3)
7. Surgical or other procedures exclusions:
 - a. Any previous rhizotomy or rhizolysis procedure, including cryoablation, RF ablation or pulsed RF on the dorsal root ganglion (DRG) or the medial branch of the dorsal ramus nerve that crosses or lies below the T8 vertebra, within one year prior to the Baseline Visit.
 - b. Anesthetic block of the DRG or medial branch of the dorsal ramus nerve that crosses or lies below the T8 vertebra or injection of epidural steroids for back pain in the 30 days prior to the Baseline Visit.
 - c. Any previous back surgery including laminectomy or discectomy at or below segmental level T8, or spinal fusion at any level.
 - d. Any previous thoracic or lumbar sympathectomy.
8. Any prior diagnosis of lumbar vertebral compression fracture, lumbar pars fracture, pars defect, or lumbar annular tear with disc protrusion that is amenable to surgery.
9. Planned surgery:
 - a. Any major surgery (including elective surgery) planned in the twelve months following the Baseline Visit (does not include minor surgeries not expected to impact the lumbar spine (e.g. colonoscopy)).
 - b. Any elective surgery of any kind (including, for example, tooth extraction, gynecological surgery, or cosmetic surgery) in the time between the Baseline Visit and the Primary Endpoint Assessment Visit.
10. Any co-morbid chronic pain conditions.
11. Other clinical conditions:
 - a. Pregnant or planning to be pregnant in the next 12 months, at the time of inclusion.^e
 - b. Pregnancy at any time in the 6 months, or lactating in the 3 months, prior to the Baseline Visit.

d The reason for exclusion of Subjects on high doses of narcotics or anti-depressants is that these doses may have altered the CNS to the extent that the therapy may not work, there is a possibility of addiction that may not resolve even after back pain symptoms are reduced or eliminated, and there is a possibility that a significant portion of the Subject's back pain symptoms are secondary to opioid induced hyperalgesia

e Subjects will be advised that if they become pregnant or plan to become pregnant after the Primary Endpoint Assessment Visit, the Activator will be withdrawn and the IPG programmed to OFF to prevent any stimulation delivery during pregnancy. The IPG may be reprogrammed and the Activator returned if the Subject requests following completion or termination of the pregnancy.

- c. Any condition unrelated to the CLBP such as muscle wasting, muscle atrophy, other disability (e.g.: paraplegic, amputee, cerebral palsy) or muscular or skeletal disease (e.g.: arthritis in trunk or limbs, multiple sclerosis, rheumatoid arthritis) which, in the opinion of the Investigator, could limit physical movement or compliance with the protocol, or interfere with the assessment of efficacy of the investigational procedure.
 - d. Poorly controlled diabetes (Type I or Type II) determined by HbA1c >8.
 - e. Past or current neurological disorders (e.g.: known multiple sclerosis, motor neuron disease, Guillain-Barré syndrome, Parkinson's, Huntington's Disease, Alzheimer's, epilepsy, stroke, brain cancer, traumatic brain injury).
 - f. Cancer requiring treatment during the study.
 - g. Any drugs (e.g.: immunosuppressive drugs) or co-morbidity that might inhibit wound healing or electrode scarring, or drugs associated with reduced effectiveness of neuromodulation for other applications.
 - h. Any medical condition requiring anticoagulation (other than aspirin) that, in the opinion of the physician prescribing the anticoagulant, cannot be safely suspended for 5 days prior to device implantation surgery and an appropriate period after implantation surgery.
 - i. Any active infection in the vicinity of the implant site or any systemic infection.
12. Psycho-social exclusions
- a. Be involved in an injury claim under current litigation.
 - b. Have a pending or approved financial compensation claim (e.g.: worker's compensation claim, long term disability claim) or any financial compensation (including social welfare payments) related to the Subject's CLBP.
 - c. Current incarceration (prison or jail)
 - d. Have an assessment of current active depression significant enough (DASS depression score >9) to impact perception of pain, compliance with intervention and/or ability to evaluate treatment outcome.
 - e. Have evidence of an active disruptive psychological or psychiatric disorder or other known condition significant enough to impact perception of pain, compliance with intervention and/or ability to evaluate treatment outcome (e.g.: active depression, bipolar disease, Alzheimer's disease) as determined by a psychologist or psychiatrist.
13. Protocol Compliance Exclusions
- a. Inability or unwillingness to comply with all protocol requirements.
 - b. Inability to maintain the prone or side lying position in a relaxed manner for the duration of each stimulation session.
 - c. Inability to operate the Activator, such as arthritis that limits arm or shoulder movement, or inability to learn how to operate.
 - d. Inability to assess changes in pain intensity or perform wound care.
 - e. Inability or unwillingness to complete the Journal.
14. General exclusions
- a. Any other active implantable device including an implantable device for back pain (such as an implantable drug pump or Spinal Cord Stimulator), pacemaker, implantable defibrillator, cochlear implant, deep brain stimulator, implantable drug pump, or other implanted neurostimulation device.
 - b. Prior exposure to an implantable neurostimulator for treatment of pain, including spinal cord stimulation (including trial implant of SCS leads), occipital nerve stimulation or peripheral nerve stimulation.
 - c. A condition currently requiring or likely to require use of MRI or diathermy while implanted with the ReActiv8.

- d. Therapy with any other investigational intervention (drugs, devices, or procedures) for the treatment of back pain at the time of the Baseline Visit, or at any time in the past if the past investigational intervention did not subsequently gain regulatory approval.
- e. Current or planned participation in any other clinical trial during participation in this Trial.
- f. Life expectancy <1 year

Table 3: Benzodiazepine Equivalents

Drug	Dose Equivalent to 15mg Diazepam (mg)
Alprazolam	1.5
Alprazolam extended release	1.5
Chlordiazepoxide	30
Clonazepam	0.75
Clorazepate	22.5
Estazolam	0.9
Flurazepam	15
Lorazepam	3
Oxazepam	45
Prazepam	45
Quazepam	15
Temazepam	15
Triazolam	0.3

5.3. Other Therapy During the Trial

5.3.1. Medication

Subjects shall be advised to not make any change to medications for treatment of low back pain at the time of the Subject's inclusion in the Trial until the Primary Endpoint Assessment Visit. This includes medications for pain and muscle relaxants. Subjects will be informed that they may reduce, increase or discontinue medications for low back pain following the Primary Endpoint Assessment Visit.

Subjects will be informed that if they believe they need any change in prescription medications for treatment of low back pain during the Trial, then they should contact the Investigator who will arrange for modification of type or dose of pain medications, as clinically necessary, and the data will be recorded. Subjects will be told that they should not request modification to prescribed drugs for their low back pain from any non-study physician during the period from baseline until the Primary Endpoint Assessment Visit. Any change in medications for other conditions (e.g.: hypertension) are allowed if prescribed by the Subject's regular treating physician.

All Subjects shall continue on any and all prescribed medication deemed medically necessary and not prescribed for the indication of CLBP (e.g.: antihypertensive medicines, statins, thyroid medications, diabetes medication, and low-dose aspirin).

Any change in pain medication prescribed and taken over the 14 days prior to the 120 day visit shall be reported by the Subject at the visit. If the prescribed dose is PRN, the Subject shall report the use of the drug over the prior two weeks if it changed from that taken at baseline.

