4.7.1.1. Hypotheses

The primary efficacy objective will be assessed by the following hypotheses:

$H_0: P_{VAS_T} = P_{VAS_C}$

$H_A: P_{VAS_T} \neq P_{VAS_C}$,

where P_{VAS_T} is the proportion of Subjects meeting primary success criteria in the Treatment group and P_{VAS_C} is the proportion of subjects meeting success criteria in the Control group. The hypotheses will be tested using a two-sided binomial test for a difference in proportions. The objective will be met if a statistically significant difference favoring the Treatment group is found.

The study will be considered a success if the primary efficacy objective is met.

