4.7.1.2. Sample Size Rationale

The sample size for the study is determined under the following assumptions for the primary efficacy endpoint:

- Minimum power of 80%
- Type I error of 5%
- Assumed primary efficacy success in Treatment group: 50%
- Assumed primary efficacy success in Control group: 25%

Under the above assumptions, a minimum of 116 evaluable Subjects is required in order to demonstrate superiority of the ReActiv8 treatment. The total sample size is increased by 10% to 128 to allow for attrition.

An adaptive statistical design using a single interim look will be used for sample size re-estimation when at least 50% of the implanted Subjects have completed the Primary Endpoint Assessment Visit. Details of the interim analysis are provided in the Statistical Analysis Plan.

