- During the clinical Trial prior to the primary outcome assessment, public information available from the Sponsor (e.g.: the web site) will be carefully worded with regard to sensations perceived with stimulation from the ReActiv8.

The primary outcome measure is average low back pain VAS completed alone by the Subject at the visits without assistance. Thus the endpoint assessment is inherently blinded since no assessor is involved.

After endpoint data collection at the Primary Endpoint Assessment Visit, all Subjects will complete a questionnaire to assess blinding. It is anticipated that the Treatment group will be

b Subjects will be advised that if they experience pain, discomfort, or any untoward effect, then they should contact the site research coordinator and not discuss with anyone else.

found to be predominantly unblinded because they will have felt muscle contraction and it is expected that those Subjects whose back pain has improved will assume they are in the Treatment group. It is anticipated that the Control group will be approximately 50% unblinded.

The blinding assessment questionnaire for Subjects is shown in Figure 4, and based on the methods suggested by Bang.⁶⁷

Do you think you were in the Treatment or Control group?		
 Treatment	 Control	 No idea
How certain are you of your answer?		
 Strongly believe	 Somewhat believe	 No idea

Figure 4: Blinding Assessment Questionnaire

The Subject may experience an adverse event that requires the Investigator to be made aware of the Subject's randomization assignment. Unblinding should only occur in circumstances where there is a risk to Subject health or safety and every attempt should be made to contact the Sponsor before unblinding the Subject's randomization assignment. In addition, every attempt should be made to keep the Subject blinded to the randomization assignment, unless the Investigator believes that the Subject should be made aware in order to manage the adverse event. If it is necessary to unblind the Subject's randomization assignment, documentation of this will be provided through a study deviation case report form.

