8.5. Primary Efficacy Endpoint

8.5.1. Primary Analysis

The Primary Efficacy Endpoint is a comparison of responder rates between Treatment and Control groups, where a “responder” is a Subject with $\geq 30\%$ reduction from baseline in average low back pain VAS, without any increase from baseline in pain medication and/or muscle relaxants prescribed and taken in the two weeks prior to the Primary Endpoint Assessment Visit.

Note: The primary outcome measure is intended to assess the efficacy of 120 days of stimulation. Thus the visit for assessment of the primary outcome must occur no sooner than 120 days post randomization.

The primary efficacy endpoint will be assessed by the following hypotheses:

$H_0: \pi_{VAS_T} = \pi_{VAS_C}$

$H_A: \pi_{VAS_T} \neq \pi_{VAS_C}$,

where π_{VAS_T} is the proportion of Subjects meeting primary success criteria in the Treatment group and π_{VAS_C} is the proportion of Subjects meeting success criteria in the Control group. The hypotheses will be tested using a two-sided binomial test for a difference in proportions. The objective will be met if a statistically significant difference favoring the Treatment group is found.

The study will be considered a success if the primary efficacy endpoint is met.

For the primary analysis in the ITT population, the impact of Subjects with missing endpoint assessment will be examined in sensitivity analyses.

Records of pain medications will be collected along with all other medications used for treatment of low back pain, which are also being collected for analysis of secondary and cost-effectiveness endpoints. The Subject will report medications taken at each scheduled follow-up visit. Rescue medications taken on an exceptional basis for acute pain conditions other than back pain will also be documented and their possible effect examined as part of sensitivity analyses.

The number and percent of randomized Subjects meeting the responder criteria will be presented by randomization group with associated 95% asymptotic confidence limits. The difference in proportions and associated 95% confidence limits will be presented along with the p-value from a binomial test for the test of the hypothesis associated with the primary objective.

The individual components of the primary efficacy endpoint (VAS and medications) will be analyzed and presented separately. Cumulative proportion of responder analysis will also be used as a way of presenting this data.

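### PRN medication change at the 120-day visit can rest on the Subject's own judgement: one rule makes the report conditional on change, and no rule fixes a Baseline quantity or defines an increase

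*Protocol*

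**What the plan says.** **Endpoint.** SAP 8.5.1, like Protocol 4.7.1, defines a responder as a Subject with at least a 30% VAS reduction, "without any increase from baseline in pain medication and/or muscle relaxants prescribed and taken in the two weeks prior" to the Primary Endpoint Assessment Visit. Protocol 4.7.6 confirms that Subjects who increase medication are classed as non-responders.

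**Entry.** Protocol 5.1, criterion 6b, Note 3: "A stable dose means the Subject reports no significant change in regular use of medications, which may include PRN use", over the 30 days before Baseline.

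**Capture of PRN use at the endpoint visit.** Protocol 5.3.1 is the only PRN-specific rule: "the Subject shall report the use of the drug over the prior two weeks if it changed from that taken at baseline". Other places carry no such condition. Protocol 4.7.1 has medications reported at every scheduled follow-up visit, 6.8 lists pain medications among the Visit 8 data, Table 2 shows a medications questionnaire at that visit, and 9.1.9 has the coordinator ask the question.

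**Baseline.** Protocol 6.1 and 9.1.9 call for the medications in use. They do not ask for a count of PRN doses or set a look-back period.

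**Blinding.** Protocol 4.9 expects the Treatment group to be "found to be predominantly unblinded because they will have felt muscle contraction", and the Control group to be about 50% unblinded.

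**The concern.** The medication rule is one of the two halves of the single confirmatory endpoint. For a fixed daily dose, an increase is easy to see. For a PRN drug it needs two comparable quantities and a rule for comparing them, and the documents supply neither. A site that follows 5.3.1 literally asks the Subject whether use has changed and records an amount only if the answer is yes. The Subject then makes the comparison from memory.

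Subjects who believe they are on active stimulation may judge or report change differently from those who do not. An increase that goes unreported leaves a VAS responder scored as a success. The record looks complete, so nothing flags it as missing. If such omissions are more common in the Treatment arm, the error favours the device.

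**Working it through.** **1. The collection rules side by side**

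| Element needed | Baseline | 120-day visit |
|---|---|---|
| Names of drugs | Yes (6.1, 9.1.9) | Yes (4.7.1, 6.8, Table 2) |
| PRN amount for every Subject | Not stated | Only if changed (5.3.1); amount not mentioned elsewhere |
| Look-back window | 30 days for stability (criterion 6b); none for PRN amount | 14 days |
| Definition of PRN increase | None | None beyond the word itself |

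The daily Journal does not fill the gap: the only Journal item listed at Visits 6 to 8 is VAS.

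**2. Would the planned analyses reveal the problem?** SAP 7.2 has a tipping-point analysis, which imputes missing primary assessments, and last observation carried forward. An unreported increase is not missing, so neither detects it. SAP 8.5.1 presents the VAS and medication components separately, but from the same records. The sample-size increase in SAP 8.7 can restore power; it cannot remove bias.

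**3. The plan's own figure.** Inputs (Protocol 4.7.1.2): 50% vs 25%, two-sided 5%, 80% power. Protocol 4.7.1.1: "The hypotheses will be tested using a two-sided binomial test for a difference in proportions". With pooled variance and no continuity correction:

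n per arm = [1.96·√(2·0.375·0.625) + 0.8416·√(0.5·0.5 + 0.25·0.75)]² / 0.25² = 57.7, so 58 per arm and 116 in total; power at 58 is 80.2%. Then 116 × 1.10 = 127.6, so 128. The plan's figures reproduce, and the point does not touch them.

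**4. Illustration of the bias.** All inputs here are assumed, because the documents give no PRN prevalence or reporting rate. Take no treatment effect, 35% VAS responders in both arms, a share f of PRN users, and 0.46 of them showing more use than at Baseline (equal Poisson means of 14 doses in 14 days; means of 4 to 28 give 0.43 to 0.47). If an arm reports a fraction r of its increases, its observed rate is 0.35·(1 − f·0.46·r).

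Probability of significance favouring Treatment = 1 − Φ[(1.96·SE₀ − d)/SE₁], at 58 per arm, where d is the difference in observed rates and SE₀ and SE₁ are the pooled and unpooled standard errors.

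- f = 0.4, Treatment r = 0.5, Control r = 1: 31.8% vs 28.6%, d = 3.2 points, SE₀ ≈ SE₁ ≈ 0.085; result 5.7%.
- f = 0.2, same reporting: 33.4% vs 31.8%, d = 1.6 points; result 3.8%.
- f = 0.4, Treatment r = 0.5, Control r = 0.75: 31.8% vs 30.2%; result 3.8%.
- Equal reporting in both arms: 2.5%.

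A second set of assumptions fixes the true composite rate at 25% in both arms and lets 10, 20 or 30% of VAS responders have an increase. With Treatment reporting half and Control all, it gives 3.7%, 5.7% and 9.4%.

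**5. Why a definition must come with better counting.** If two 14-day counts were taken and any excess scored as failure, an unchanged PRN user would fail by chance about 46% of the time. Multiplying 50% and 25% by (1 − f·0.46) for f = 0.2, 0.4 and 0.6 gives 45.4/22.7, 40.8/20.4 and 36.2/18.1%, with power at 58 per arm of about 74%, 67% and 59%. This assumes that 50% and 25% make no allowance for such failures.

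**The case against.** Much can fairly be said for the plan.

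- Medications are collected at Visit 8 without condition in several places, and a coordinator asks. This stands: the documents contain two inconsistent capture rules, not a single conditional one. But none of the unconditional rules asks for a PRN amount or supplies a Baseline comparator.
- Exclusions 6a, 6b and 6e need daily opioid and diazepam-equivalent amounts at Baseline. True, but they do not cover other pain drugs or a 14-day window. The case report forms, which were not available for this review, may record more.
- Recall need not be long. On-target timing from Baseline to Visit 8 is about 135 to 179 days (1 to 45, plus 14, plus 120). The longest permitted interval is 232 days (45 + 17 + 30 + 140), which requires every delay at its maximum. Medications are also recorded at Visits 2, 6 and 7, and Protocol 6.15 has Subjects reminded to keep pain medication as at baseline. Those records help only if they hold PRN amounts, and the reminder could itself prompt an answer of no change.
- Control is also expected to be partly unblinded, so reporting may differ little between arms. This stands, and is why no single bias figure can be given.
- A lenient entry screen and a strict endpoint rule serve different purposes and different periods. This stands: they do not contradict each other. Entry simply admits PRN fluctuation that the endpoint rule, read strictly, would penalise.

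**Conclusion.** The point holds as a gap in capture and definition. Protocol 5.3.1 conflicts with 4.7.1, 6.8 and Table 2, no PRN quantity over a matching window is required at Baseline, and a PRN increase is undefined. Given the unblinding that the protocol itself expects, this part of the primary endpoint can rest on a possibly arm-dependent judgement by the Subject, and the missing-data analyses would not show it.

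The size is not computable from the documents. With 20–40% PRN users, Treatment reporting half of its increases and Control all, false success in favour of the device is about 4–6% instead of 2.5%. With equal reporting there is no inflation.

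A reader might infer three stronger things that the documents do not support:

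- **That PRN use is captured only when the Subject believes it changed.** The unconditional collection rules say otherwise.
- **That the current plan loses power to 59–74%.** That loss needs two dose counts, which the plan does not require. It may also double-count, because 50% and 25% are stated as success rates on the composite endpoint.
- **That bias toward the device is established.** Unblinding is the protocol's expectation, and differential reporting is an assumption.

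**What to change.** Make these changes together:

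1. Delete the if-changed condition in Protocol 5.3.1 so that it agrees with 4.7.1 and 6.8.
2. At Baseline and Visit 8, record for every Subject the number of doses of each PRN prescribed pain medication and muscle relaxant taken in the prior 14 days.
3. Derive increase from those two records by program, or by a person blinded to arm.
4. Pre-specify in the SAP, before unblinding, how increase is defined for PRN use, and report strict any-increase scoring as an alternative analysis. This is not optional: items 2 and 3 without it would score ordinary fluctuation as failure, as step 5 of the working shows.

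The change affects only recording and classification, not what Subjects may take. The cost is a field on an existing questionnaire, a slightly longer medication interview at two existing visits, and a wording change in the protocol and SAP.
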